#### Interaction with the SYD application

Participants in the Control Group (Group B) will be invited to install and interact with the SYD smartphone mHealth app at Month 4. Participants in the Intervention Group (Group A) will be invited to install and interact with the SYD smartphone mHealth app at Baseline.

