### 10 Statistics and data analysis

### **10.1 Data handling and analysis**

Study data will be collected via the Qualtrics online website built for this study. The Qualtrics survey software has advanced analytics tools built online and analyses will only be descriptive. Data will be analysed by Investigators at the Sponsor organisation (Southern Health NHS Foundation Trust). No data queries will be raised for participants.

Primary endpoint analysis will be undertaken using data collected throughout a period of 3 months of SYD application usage by the study participants. Further analysis of longer-term effects will be undertaken at 6 months after the participant first interacted with the SYD application.

WHOQOL-BREF surveys will be scored according to the general guidelines (World Health Organization, 1996), deriving scores for the 4 main domains (Physical health, Psychological, Social relationships and Environment).

EQ-5D-5L surveys will be scored according to the general guidelines (Herdman et al., 2011), deriving scores for the 5 main domains of the instrument (Mobility, Self-Care, Usual Activities, Pain/Discomfort and Anxiety/Depression), and

Title: Pilot	Title: Pilot evaluation of a personalised, prevention mHealth partner, SYD, and its impact on Quality of Life of NHS staff								
Authors	[name], [name], [name], [name], [name]	Ver.	2.0	Date Authorised	13/04/2022	Page 16 of 24			

SYD (See Yourself Differently) for NHS the 1-dimensional EQ VAS. An EQ-5D index value will be derived from EQ-5D-5L scores using the latest value set for England (Devlin et al., 2018).

PSS-4 scores will be derived according to the general guidelines (Cohen, 1988).

HADS scores will be subdivided into anxiety (HADS-A) and depression (HADS-D) subdomains and scored according to general guidelines (Zigmond et al., 1983).

WHOQOL-BREF, 5Q-5D-5L, EQ-5D index, HADS-A, HADS-D and PSS-4 scores will be modelled using linear mixed effects models. These models will be used to test the effect of group, time of measure and app-related metrics such as type of recommendations done by participants and level of interaction with the SYD app. Baseline characteristics of participants will be used to adjust the models. Imputation procedures will be used to impute missing values where deemed plausible. Effect size measures and p-values will be reported for all group comparisons. The Null hypothesis is of no significant change in Quality of Life.

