#### SYD (See Yourself Differently) for NHS 12.3 Data sharing

The study is a research collaboration between Southern Health NHS Foundation Trust (Sponsor) and iamYiam, a company developing and testing the SYD application. Southern Health NHS Foundation Trust and iamYiam have entered into a collaboration agreement stating their responsibilities in connection with this study. Both parties have Data Controller responsibilities in relation to their respective datasets generated by this study. Data will not be shared with anyone outside of the Sponsor and iamYiam research project teams, unless needed to independently verify results at the request of regulators.

All study participants will be allocated a randomised study number at the time of joining the study. A record of participant study numbers linked to participants names and email addresses will be kept in a password protected document on the Sponsor's drive, with access strictly restricted to identified members of the research team. The primary endpoint analysis will be carried out by the Sponsor using data collected on the study website.

The Sponsor shall transfer pseudonymised study data via a secure transfer method to iamYiam for analysis and for the purpose of further research related to the SYD application use. The research study data sharing plan will be detailed on the Participant Information Sheet (PIS) and specific consent sought as part of the informed consent process.

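### Section 10.1 reads as testing allocated group and post-randomisation app use in the same mixed models; with uncentred, zero-for-controls coding the group estimate can be biased in either direction

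*Protocol*

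**What the plan says.** Section 10.1 lists the quality-of-life, HADS and PSS-4 outcomes and states that their "scores will be modelled using linear mixed effects models". It continues that these same models are to "test the effect of group, time of measure and app-related metrics", and gives as examples "type of recommendations done by participants and level of interaction with the SYD app". The only terms it describes as adjustment are baseline ones: "Baseline characteristics of participants will be used to adjust the models". Effect sizes and p-values are promised for every comparison between groups. The section names no model without the app metrics and gives no coding for them in people who have no app. It does not label them exploratory or confine them to SYD users.

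Section 6 fixes who can have app use. For the intervention arm, "Participants in the Intervention Group (Group A) will be invited to install and interact with the SYD smartphone mHealth app at Baseline". For the control arm, "Participants in the Control Group (Group B) will be invited to install and interact with the SYD smartphone mHealth app at Month 4". The primary window in Sections 3.2 and 3.7 is 3 months.

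Section 12.3 bears on the data source: "The primary endpoint analysis will be carried out by the Sponsor using data collected on the study website". App data are a separate dataset, for which the app company is Data Controller (Section 12.1).

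**The concern.** The randomised question is what allocation to SYD does to quality of life over 3 months. App use is a consequence of allocation and plausibly the route by which SYD works. In the primary window it can be non-zero in one arm only. Conditioning on it in the model that yields the group contrast changes what that contrast means. Part or all of a real benefit can move into the use coefficient. If people with better or worse underlying quality of life use the app more, the group coefficient also picks up that selection, and randomisation no longer protects it. An SAP that follows Section 10.1 literally would carry this into the primary result, and the p-value for group would be reported from it.

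**Working it through.** **Inputs from the protocol.** 250 evaluable per arm (Section 3.9), 1:1 allocation (Section 3.5), app access for controls only from Month 4 (Section 6). The protocol gives no effect size, SD, distribution of app use or relation of use to prognosis, so it has no figure of its own to reproduce. Everything below rests on assumed values.

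**Assumed inputs.** Outcome in SD units; true total effect of allocation 0.30 SD or 0; use right-skewed with mean 1 in the intervention arm and 0 in controls; share of the effect acting through use 0, 0.5 or 1; correlation of use with stable prognosis 0, +0.3 or -0.3.

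**Algebra.** All controls have use = 0, so the slope on use is learned from the intervention arm. To a close approximation, then:

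group coefficient with use in the model = group difference without it - (slope on use x mean use)

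With mean use 1, the slope is 0.30 x share + d. Here d is the association of use with outcome that comes from prognosis alone. In the simulations d is about +0.15 at correlation +0.3, 0 at correlation 0 and -0.15 at correlation -0.3. Hence:

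| Share through use | Correlation | Group coefficient |
|---|---|---|
| 0 | 0 | 0.30 - 0 - 0 = 0.30 |
| 0.5 | 0 | 0.30 - 0.15 - 0 = 0.15 |
| 1 | 0 | 0.30 - 0.30 - 0 = 0.00 |
| 0.5 | +0.3 | 0.30 - 0.15 - 0.15 = 0.00 |
| 1 | +0.3 | 0.30 - 0.30 - 0.15 = -0.15 |
| 1 | -0.3 | 0.30 - 0.30 + 0.15 = +0.15 |

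**Simulation.** Two set-ups agree with the table to about 0.01 SD.

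- *Set-up A*: mean of Months 1-3 adjusted for Month 0, within-person correlation 0.6, coefficient of variation of use 0.6, 2,000 trials per scenario. Without the metric, group is 0.30 SD (SE 0.056), rejected in about 100% of trials. With the metric, all through use and correlation 0, it is 0.00 SD (SE 0.085), rejected in about 5%. At correlation +0.3 it is -0.15 SD, significant in the wrong direction in about 40%.
- *Set-up B*: a single follow-up adjusted for baseline, correlation 0.5 with baseline, 400 trials per scenario. Without the metric, group is 0.295-0.307 SD in every scenario with an effect (SE 0.08). With it the SE is 0.115.

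**No true effect, correlation +0.3.** The group coefficient is about -0.15 SD in both set-ups. In A, -0.15/0.085 = -1.76, so the chance of falling below -1.96 is about 42%. In B, -0.152/0.115 = -1.32, giving about 26% (25% simulated). Without the metric, rejection is about 4-6.5%.

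**Mixed-model checks.** With 40 random-intercept fits per scenario and all of the effect through use, group went from 0.28 to -0.02 SD at correlation 0 and from 0.29 to -0.17 SD at +0.3. In a version where use varied month to month (12 fits, illustrative only), the coefficient with use was 0.01 SD at correlation 0 and -0.07 SD at +0.3. The size of the shift therefore depends on how use is summarised.

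**Coding.** In Set-up B, centring use within the intervention arm and setting controls to 0 left the group coefficient equal to the one without the metric (0.295-0.307 SD) in every scenario with an effect.

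**The case against.** The sentence in Section 10.1 can be read as a list of questions, each with its own model, rather than as one formula. Only baseline characteristics are called adjustment. Section 12.3 bases the primary analysis on study-website data, which on its face leaves the metrics out. The design also has a before-and-after element, and engagement is a secondary objective, so app metrics have a proper place in some analysis. Exact model terms and coding are often settled in an SAP. The study is a pilot sized for precision, and Section 10.1 itself also calls the analyses descriptive.

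Much of this stands. The bias may never reach the primary result if Section 12.3 governs. What remains is that Section 10.1 makes a positive statement in which a single family of models serves all three kinds of term, names no model without the metrics, and sits awkwardly with Section 12.3. An SAP cannot follow both for the primary model. Pilot status does not remove the problem while effect sizes and p-values for group are promised.

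A reader might go further and infer that the group coefficient necessarily stops estimating the SYD effect. The documents do not support that: it depends on a coding they do not state, centred coding leaves the estimate intact, and there is no bias if the effect does not run through use and use is unrelated to prognosis. Nor does any text say that use would be coded missing for controls, so the loss of every control row is only a possibility. The bias is not always downward either: a negative use-prognosis correlation pushes the estimate up.

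**Conclusion.** The point holds conditionally. On its plain reading, Section 10.1 tests group alongside post-randomisation app use, which controls cannot have in the primary window. If use enters uncentred and zero for controls, the coefficient is a contrast at zero use. Among the scenarios tabulated above it runs from the full 0.30 SD down to -0.15 SD for a true effect of 0.30 SD. With no effect it can raise false rejection from about 5% to about 25-42% at a correlation of +0.3. Direction and size depend on assumed mediation, assumed correlation and the coding and timing of the metric. None of these is in the protocol, so the figures show what could happen, not what will. What is firm is that Sections 10.1 and 12.3 need to be reconciled before the primary analysis.

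**What to change.** In Section 10.1, consistent with Section 12.3, state that the primary randomised comparison (Months 0-3, participants as randomised) contains allocated group, time, group-by-time and pre-randomisation covariates only, and no app-derived post-randomisation variable. Name covariates that are collected in both arms before randomisation. Section 6 places age, sex, ethnicity and medical conditions in the app at first use, which for controls is Month 4 or later. Put recommendations done and level of interaction in a separate analysis, labelled exploratory, within SYD-exposed data. The cost is a wording change in the protocol, carried into the SAP, and one additional exploratory model; sample size and the scheduled questionnaires are unaffected.

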QoL is closely related to physical and mental health, as individuals living with conditions such as obesity (Sach et al., 2007), diabetes, cardiovascular risk factors (Sullivan et al., 2007), anxiety (Olatunji et al., 2007), stress (de Frias et al., 2015) and depression (Ruo et al., 2003), consistently report lower levels of QOL. Lifestyle interventions such as supervised exercise training (Eriksson et al., 2010) or personalised counselling (Lindström et al., 2006), have shown success in increasing and sustaining individual's QOL in the long run, however, these interventions frequently report reduced effectiveness due to poor attendance and adherence rates.

Several factors have been identified to predict lower adherence to lifestyle interventions, including unrealistic expectations, lower baseline mood or gaps in knowledge (Burgess et al., 2017). Indeed, behavioural treatment strategies such as self-monitoring (Mahoney et al., 1973), self-reinforcement and goal-setting with specific, measurable, attainable, realistic and time-framed goals (Bovend'Eerdt et al., 2009), have been shown to be some of the most important drivers in improving adherence to lifestyle modifications with behavioural change most likely to be achieved when it is self-motivated, personalised to each individual and rooted in positive thinking (World Health Organization, 2003).

To tackle these issues, mobile health (mHealth) interventions can provide a solution to increase individual's adherence to health and wellbeing recommendations (Vlahu-Gjorgievska et al., 2018). The widespread use of smartphones, as well as integration with other health-oriented devices, such as fitness trackers, allows for recommendations to be personalised based on each individual's lifestyle patterns, personality, environment, personal choices and goals. In turn, individuals are more likely to be engaged with their own progression towards significant behavioural changes, with the ultimate goal to increase their quality of life over the long term.

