### 2.4 SYD's evidence-based personalised lifestyle recommendation model

Our research evidence framework employs a strict assessment of the scientific evidence for each actionable recommendation within SYD, accounting to an evidence base of >2,500 meta-analyses and systematic reviews evaluating results of >10,000 research papers. Peer-reviewed articles are automatically fetched, scored and prioritised based on article-level metrics (normalised citation-based and altmetrics). These are analysed and curated by a team of expert scientists to validate and extract relevant features such as effect and population sizes, inclusion/exclusion criteria and demographics of the groups. Evidence for effect of lifestyle interventions on a given health dimension are then aggregated and normalised effect sizes are used to estimate the change attributed to an individual performing a recommended action. These are normalised to account for the frequency and amount that individuals perform the recommended action, which is estimated by feedback and scheduling through the SYD app. To estimate the current health states of the individual, SYD uses AI state estimation models (multidimensional Kalman filters) accounting previous state estimations, covariance between states and uncertainty through time.

By analysing each individual's past behaviour and preferences, and using aggregated data from similar users, SYD's recommender system predicts and presents lifestyle recommendations for which the individual is more likely to be interested and act on, and which are expected to have the most significant impact on their wellbeing. Each recommendation is presented in a succinct manner while providing information of the scientific evidence (references and abstract links and a simplified summary of that evidence), driving those recommendations. Information on which LQIs are expected to be affected and the estimated mean effect and timeframe of those changes are also shown. By interacting with SYD and performing recommendations, the user can track their progress through each LQI in an intuitive way (with training to enable this), allowing them to observe the effect of behavioural changes through time.

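### App use and recommendation type are tested as effects alongside allocation, but neither is randomised, so either can look significant, in either direction, when SYD does nothing

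*Protocol*

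**What the plan says.** Protocol section 10.1 specifies linear mixed effects models for the quality-of-life, HADS and PSS-4 scores, and then states: "These models will be used to test the effect of group, time of measure and app-related metrics such as type of recommendations done by participants". The app metrics named in full are "type of recommendations done by participants and level of interaction with the SYD app". Allocation and two behaviours that arise after allocation are thus named in one sentence as effects to be tested. Nothing in the section calls the app-metric results exploratory or associational, or says they are fitted separately from the group comparison. The only stated safeguard is "Baseline characteristics of participants will be used to adjust the models", and those characteristics are not specified.

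Other sections describe what drives the two metrics:

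- Section 2.2: "Several factors have been identified to predict lower adherence to lifestyle interventions, including unrealistic expectations, lower baseline mood or gaps in knowledge".
- Section 2.4: SYD estimates the user's current health state. Its "recommender system predicts and presents lifestyle recommendations for which the individual is more likely to be interested and act on", and it favours those "which are expected to have the most significant impact on their wellbeing".
- Sections 3.5 and 5.1: people with low anxiety are said to engage poorly with wellbeing measures, and those within the HADS entry range are expected to engage most.

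Section 6 gives the Control Group access to SYD only from Month 4.

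**The concern.** A coefficient for level of interaction compares people who chose to use the app more with people who chose to use it less. If that choice depends on mood, the coefficient reflects who uses SYD as well as anything SYD does. For recommendation type the problem is confounding by indication and selection: SYD offers recommendations partly according to estimated state and expected benefit, and the participant then decides which to carry out.

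Mood and wellbeing overlap with the outcomes: the psychological domain of WHOQOL-BREF, the anxiety/depression item of EQ-5D-5L, HADS and PSS-4. Adjusting for a Month 0 score helps, but not fully. One score measures a person's stable level with error, and it cannot capture mood that changes after baseline and alters use.

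At stake is interpretation. A significant use coefficient reported as a tested effect could be read as SYD working, or failing, in those who engage. Section 20 anticipates discussion with regulators of new claims for SYD, so a misreading could have consequences.

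**Working it through.** **No plan figure to reproduce.** The protocol states no alpha, effect size, SD or use-mood correlation. Its only relevant number is the target of 250 evaluable participants per group (section 3.9). The rest is assumed: a two-sided 5% test, outcome SD 1, and a within-person correlation of 0.6 (stable variance 0.6, residual variance 0.4). The true SYD effect is zero. U is use, with SD 1 and correlation r with mood. Only the 250 Intervention participants are used.

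**Quantities.** Let Y be the mean of Months 1-3 and Y0 the Month 0 score. With balanced data, a between-person coefficient in a random-intercept model equals that from regression on person means.

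- Var(Y) = 0.6 + 0.4/3 = 0.733
- corr(Y, Y0) = 0.6/√0.733 = 0.701, whose square is 0.491

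**Case A: use linked to the stable level.** corr(U, Y) = r√(0.6/0.733) = 0.905r, and corr(U, Y0) = r√0.6 = 0.775r. The partial correlation given Y0 is
(0.905r − 0.775r × 0.701) / √[(1 − 0.6r²)(1 − 0.491)].

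**Case B: use follows mood in Months 1-3.** corr(U, Y) = r and corr(U, Y0) = 0.701r. The partial correlation is
r(1 − 0.491) / √[(1 − 0.491r²)(1 − 0.491)].

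**False-positive rate.** Approximately P(|Z + atanh(ρ)√d| > 1.96), where ρ is the correlation or partial correlation, d = 247 unadjusted and d = 246 with Y0 in the model. For r = 0.2 in Case A adjusted: ρ = 0.103, atanh(ρ) × √246 = 1.62, and P(Z > 0.34) = 0.37.

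| Absolute r | A, unadjusted | A, Month 0 adjusted | B, Month 0 adjusted |
|---|---|---|---|
| 0 | 5% | 5% | 5% |
| 0.1 | 30% | 13% | 20% |
| 0.2 | 82% | 37% | 62% |
| 0.3 | 99% | 70% | 94% |

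Simulations of the same set-up agree to within about two points. One set gave 13 / 36 / 68% for A adjusted and 19 / 64 / 95% for B.

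**Sign.** The rates depend on |r|, so r = −0.2 rejects as often as r = +0.2, but the slope runs against SYD. In Case A adjusted, the false slope is r√0.6 × (1 − 0.6)/(1 − 0.6r²). At r = ±0.2 that is ±0.064 SD of outcome per SD of use.

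**Sensitivity to the mechanism.** In a separate simulation that included both groups and linked use to each person's own mood change, the Month 0 adjusted rates were 24% at 0.2 and 48% at 0.3. The rate therefore depends on how use and mood are linked as well as on r.

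**The randomised comparison.** In those simulations, with no SYD effect, a model with group and no app metrics rejected in 3.7% to 5.7% of runs, and in 4.3% to 5.9% with the Month 0 score added.

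**The case against.** **What stands.** The direction of bias is not established. Section 2.2 implies that people in lower mood use the app less, which would favour SYD. Sections 3.5 and 5.1 suggest that less anxious people engage less, which would count against it. The two could partly cancel, and at zero correlation there is no artefact. All correlations above are assumptions. Case B builds the association in by construction: it shows what reverse causation would do, not that it occurs. Section 10.1 promises p-values for group comparisons, not explicitly for app metrics, and also describes the analyses as only descriptive. The study calls itself a pilot.

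**What does not answer the point.** The same section commits to testing the effect of these metrics, so its descriptive label and its model specification need reconciling. Leaving detail to a SAP does not help, because the protocol itself fixes the metrics as tested effects. The secondary objective on engagement can be met by description.

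**Stronger readings that the documents do not support.**

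- A reader might infer that a dose-response in SYD's favour will appear even if SYD does nothing. The documents support only that a false association can appear, in either direction.
- A reader might infer that mood and targeting determine use. Section 2.4 describes which recommendations are presented, not how much the app is used.
- A reader might infer that the randomised comparison is itself biased. That would need use and group in one model. Control use is zero before Month 4, so the group coefficient would become a contrast at zero use. With an assumed mean use of 2 SD and r = 0.2 with stable mood, the simulated bias was about −0.31 SD, or −0.13 SD with Month 0 adjustment. Section 10.1 does not say the terms share a model, and section 12.3 bases the primary analysis on study-website data, whereas app data are held on the company's platform. This is a reason to state the separation, not evidence of bias.

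**Conclusion.** The point holds as a limited one. Section 10.1 presents two non-randomised, post-allocation behaviours as effects to be tested, with no associational label, while sections 2.2 and 2.4 give plausible routes from mood or health state to both. A test of those terms does not hold its nominal error rate as a test of what SYD does unless use is unrelated to mood given the adjustment.

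Under the stated assumptions, an absolute correlation of 0.1 raises the false-positive rate from 5% to about 13% (Case A) or 20% (Case B) after Month 0 adjustment. A correlation of 0.3 raises it to about 70% or 94%. These figures are conditional on a correlation of unknown size and sign and do not predict this trial's result. They were computed for level of interaction; the argument for recommendation type is qualitative. The group comparison, fitted as randomised without app metrics, keeps about 5%.

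**What to change.** In section 10.1, limit the tested effects to group, time and their interaction, estimated as randomised and with no app metrics in that model. Reconcile this with the statement in the same section that analyses are only descriptive.

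Report level of interaction and type of recommendations in a separate analysis, within SYD-exposed data, labelled as exploratory, non-causal associations and not as effects of SYD.

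A complier-average estimate with allocation as instrument is optional. If it is used, define use as any use of SYD, or state that a higher threshold assumes no effect of use below it. State also the assumption that allocation acts only through use, which expectation effects could break in a non-blinded design.

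The cost is a wording change and a separate descriptive analysis. The downside is that the trial gives up inferential claims about dose or recommendation type. The optional complier estimate would also have a wider interval than the group comparison and could not answer either of those questions.

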### 3.6 Trial Schema

### 3.7 Primary Endpoints

Determine the impact of SYD on Quality of Life of NHS Staff over 3 months, as measured through:

- 1. WHO Quality of Life-BREF (WHOQOL-BREF) survey (Global QOL)
- 2. EuroQoL EQ-5D-5L (Health-related QOL)

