### 3.9 Statistical analysis and sample size calculation

Approximately 3,500 NHS staff, 18 years and over, who took part in the PIoC19 study, and provided consent to be contacted will be invited to join the SYD for NHS trial.

We estimate that ~800 NHS staff will be interested and eligible to participate. As it is currently not known how many participants are likely to interact sufficiently with SYD and provide sufficient trial data, we have assumed that up to 800 participants will have to be randomised to achieve a target of 500 evaluable participants, 250 in each group. Data on all randomised participants will be evaluated and the drop-out rate in the intervention group will be determined.

As this is a pilot study to evaluate the impact of SYD, and not a superiority trial, we have estimated 500 patients being available to have reasonable confidence intervals of any changes in quality of life scales, if available. A previous study of the eBalance app showed significant lifestyle changes within 14 weeks in 85 participants with only 56 participants using the app (Safran Naimark, 2015).

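### Section 10.1 states the null as change in quality of life and ties the primary analysis to SYD use, not to the randomised Month 0–3 comparison, and names no primary score

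*Protocol*

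**What the plan says.** Section 3.7 gives the primary endpoint as "Determine the impact of SYD on Quality of Life of NHS Staff over 3 months", measured by two instruments, WHOQOL-BREF and EQ-5D-5L. No score from either is singled out.

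Section 10.1 then makes these statements:
- On the data: "Primary endpoint analysis will be undertaken using data collected throughout a period of 3 months of SYD application usage by the study participants".
- On the models: "These models will be used to test the effect of group, time of measure and app-related metrics".
- On reporting: "Effect size measures and p-values will be reported for all group comparisons".
- On the hypothesis: "The Null hypothesis is of no significant change in Quality of Life".
- Earlier, in a sentence whose subject is the Qualtrics software: "analyses will only be descriptive".

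Section 10.1 derives four WHOQOL-BREF domain scores, five EQ-5D-5L dimension scores, the EQ VAS and an EQ-5D index.

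Sections 3.5, 6 and 7 give the control group SYD only from Month 4. Section 3.5 describes a before-and-after element, notes that COVID-19 levels will vary during the study, and says the design should separate the value of SYD from effects of time and surroundings. Section 3.9 calls the study a pilot, "not a superiority trial, we have estimated 500 patients being available to have reasonable confidence intervals".

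**The concern.** A null hypothesis fixes what a rejection means. Here a rejection would mean that quality of life changed, not that it changed more with SYD than without. Scores can move over three months for reasons shared by everyone enrolled: the course of the pandemic, season, or the after-effect of selecting people on a HADS score of 8 to 14. The word significant also has no place in a null, because it describes a test result and not a population quantity.

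The description of the primary data does not repair this. During Months 0–3 only the Intervention Group uses the app, so a primary analysis defined by app use has no natural place for the controls' Months 0–3 data, which are the data that make the trial controlled.

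Separately, with two instruments, many scores and no designated primary, a favourable p-value on any one of them could be presented as the primary result. Section 19 foresees the findings being used in guidance discussions with NHS executive bodies, and Section 20 mentions possible new claims for SYD, so the distinction has consequences.

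**Working it through.** **The plan's own figure.** Section 3.9 expects up to 800 randomised to give 500 evaluable, 250 per group: 500/800 = 0.625, an implied loss of 37.5%. The arithmetic is consistent. No alpha, power, SD or target precision is given, so 500 cannot be derived from stated inputs. For orientation, 250 per arm gives an unadjusted 95% CI half-width for a group difference of 1.96 × √(2/250) = 0.175 SD.

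**1. Test of change in one arm when SYD has no effect.**

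Inputs: n = 250 (Section 3.9). Assumed, because the protocol gives none: two-sided alpha 0.05, drift of 0.1, 0.15 or 0.2 SD, and baseline–follow-up correlation r = 0.5 to 0.7.

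In baseline-SD units, SE = √(2(1 − r)/n). With λ = drift/SE, P(reject) = Φ(λ − 1.96) + Φ(−λ − 1.96).

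Example: r = 0.5 gives SE = √(1/250) = 0.0632. For drift 0.15, λ = 2.37 and P(reject) = 0.660.

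| Drift (SD) | r = 0.5 | r = 0.6 | r = 0.7 |
|---|---|---|---|
| 0.10 | 0.353 | 0.424 | 0.532 |
| 0.15 | 0.660 | 0.755 | 0.865 |
| 0.20 | 0.885 | 0.942 | 0.983 |

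For the difference between randomised groups at Month 3, the same drift enters both arms and cancels, so the rejection rate stays at 0.05.

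**2. Number of scores from the primary instruments.**

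4 WHOQOL-BREF domains + 5 EQ-5D-5L dimensions + 1 index = 10. Adding the EQ VAS gives 11. The VAS is derived, but the sentence listing what is modelled does not name it separately, so the count is 10 or 11.

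**3. Chance of at least one p<0.05 with no effect, one group comparison per score, assumed alpha 0.05.**

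- Independent scores: 1 − 0.95^10 = 0.401 and 1 − 0.95^11 = 0.431.
- Equally correlated scores (simulated normal test statistics, 400,000 draws):

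| Correlation | 10 scores | 11 scores |
|---|---|---|
| 0.3 | 0.3505 | 0.3732 |
| 0.5 | 0.2866 | 0.3048 |
| 0.7 | 0.2134 | 0.2237 |
| 0.9 | 0.1280 | 0.1317 |

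**4. After naming one score per instrument.** Two unadjusted tests, if independent: 1 − 0.95² = 0.0975. At 0.025 each the bound is 0.05.

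**The case against.** The strongest reply is that Section 10.1 does plan a controlled comparison. The models include group, p-values are promised for group comparisons, baseline characteristics are adjusted for, and Section 3.5 says the controls supply comparison data. Shared drift cancels in all of that. This stands. A reader might infer that the plan will report drift as a SYD effect, but the documents do not support that. They show only that the null and the primary data are not tied to the comparison that prevents it.

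The drift sizes are assumptions, and the result depends heavily on them, as the table shows. That also stands, which is why a range is given.

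Four further readings are tempting and should be resisted:
- That Section 10.1 flatly contradicts itself by calling the analysis descriptive and then testing. The phrase may describe only the Qualtrics tools. It sits awkwardly with the tests, but it is an ambiguity.
- That every score is tested at each of three visits, giving 33 tests. The plan is for mixed models across visits, and no visit-by-visit testing is stated.
- That confidence intervals are ruled out. Effect size measures do not exclude them, and Section 3.9 anticipates them.
- That the global label on WHOQOL-BREF promises a total score, or that the order of the two instruments was meant as a testing order. Neither is claimed.

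Finally, a multiplicity rule may properly sit in a statistical analysis plan that is not shown, and a pilot need not make confirmatory claims. Both are fair. Neither mends a null that the protocol itself states without a comparator, or a primary endpoint left as two whole instruments.

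**Conclusion.** The point holds in this form: the protocol states its null as change and defines its primary data by app use, and neither is linked to the randomised Month 0–3 comparison that the trial was built to provide. This is a wrongly stated rule, not just missing detail, and taken literally it works against the aim in Section 3.5. A valid contrast is already in the planned models, so the fault is one of designation and is easily mended.

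The exposure is conditional. If the stated null is tested as change in one arm of 250, false rejection ranges from about 35% (drift 0.1 SD, r = 0.5) to 98% (drift 0.2 SD, r = 0.7); the drift, the correlation and the 0.05 level are all assumed. If group comparisons are used without a named primary score, the chance of at least one nominally positive result is at most 40–43% under independence. It falls to about 13% if the scores are very highly correlated.

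**What to change.** 1. Restate the primary null as zero difference between the randomised groups in mean score at Month 3, adjusted for the Month 0 score. Define the primary data as Months 0–3 from both groups.
2. Name one primary score per instrument at Month 3. Then either split alpha or apply Holm across the two, or report both as estimates with 95% CIs and no confirmatory claim, which suits the pilot aim. Label all other scores and visits supportive.
3. Limit the descriptive-only statement to the Qualtrics summaries.
4. Label before-and-after results and Month 6 results as having no untreated comparison group, since controls have SYD from Month 4.

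Cost: protocol wording before analysis, and fewer results that can be called primary. If alpha is split, some power goes too: for an illustrative difference of 0.25 SD with 250 per arm, power is 79.8% at 0.05 and 71.0% at 0.025. The estimation option avoids that loss.
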